5.1.8 Other potential biases

Controls could come from different source populations with varying risk for infection with influenza or SARS-CoV-2, varying probability for acquiring influenza or COVID-19 vaccination, etc. (e.g. depending on time of year). Time (onset date) will be used to adjust for seasonal differences. Analyses will also be stratified by time (e.g. onset quarter). For COVID-19, the success of vaccination programs in some countries has resulted in only a small proportion of population remaining unvaccinated. This population may be different from the general population. Rather than using unvaccinated as the reference group in CVE, analyses using relative VE (e.g. booster vaccination compared to primary course vaccination) could be considered, although a simulation study is recommended to understand the implications of this analysis in a multicentre context.

- *Each country to describe timeline of vaccination and vaccine coverage for different target groups.*

5.2 Representativeness of subjects included in the study

The study includes cases that are consulting GPs for influenza-like or COVID-19-like symptoms. Containment and mitigation strategies for the COVID-19 pandemic may differ by country depending on the case management strategy (e.g. recommendation of contacting a specific COVID-19 helpline, or consulting a GP or health centre by telephone first). In some cases, the management strategy will have an impact on which patients consult a GP and are swabbed. This also may have an impact on the time lag between the onset of symptoms and respiratory specimen collection, and currently we do not know if this may affect false negativity rates. Beside the collection of the aforementioned data in the protocol, case-containment/mitigation/healthcare-seeking strategies should be described for each country. Note that the test-negative design adjusts for case management strategies, e.g. patients with contact to a confirmed case, as both cases and controls come from this population.

Some countries will have parallel diagnostic pathways, e.g. patients with respiratory symptoms self-referring to COVID-19 centres and patients being swabbed by GPs. This could cause a lack of representativeness among those participating in the study. This will have the most impact on VE if this is differential by case and vaccination status.

There may be country-specific recommendations on rapid antigen test use for SARS-CoV-2, which may vary by different age groups and across different time periods. If rapid antigen tests are used in the study for determining

case status, the recommendations for use should be described and sensitivity analyses excluding patients tested with rapid antigen test carried out.

With the widespread use of rapid antigen tests, it may be that patients consult a GP to confirm a positive rapid antigen self-test. Conversely, it may be that patients consult a GP only if the rapid antigen self-test was negative. If rapid antigen test positivity is associated with vaccination status, the CVE may be biased.

In certain age groups, particularly older age groups, vaccination coverage is extremely high, reaching over 95%. Such high coverage, besides affecting sample size, renders the representativity of unvaccinated controls questionable. In this situation, analyses using relative VE (e.g. booster vaccination compared to primary course vaccination) could be considered (see 5.1.8).

Annex 1. List of variables, definitions, and coding: minimum dataset

The following list of variables constitutes the proposed dataset of an IVE/CVE study at primary care level. Variables in green are optional. Study sites may not be able to collect all the proposed data and can list the variables collected in the study-specific annex.

Study sites can follow this variable naming and coding, or are welcome to code variables and values in their own way.

- *Study sites can use Table A1 below to indicate which variables they are collecting and data sources.*
- *Study sites to indicate all modifications in the variables collected and coding compared to variables below.*

Table A1. List of variables, including values, coding, and definitions

Variable name	Collected by study site? (Please also indicate data source if not patient interview)	Type	Values and coding	Definition
Study-related variables				
participate		Numeric (binary)	0 = No 1 = Yes	Agrees to participate
id		Type of variable at discretion of site	[needs to be unique]	Unique and persistent identifier for each record
gpcode		Type of variable at discretion of site	[needs to be unique]	Unique identifier for each GP
Optional				
refuse		Text		Reasons for refusal to participate
Demographics				
age ⁷		Numeric (continuous)	Integer	Age of each participant in years
sex		Numeric (binary)	0 = female 1 = male	Sex of study participant
Signs and symptoms				
onsetdate		Date	dd/mm/yyyy	Date of onset of symptoms
fever		Numeric (categorical)	0 = No 1 = Yes 8 = Do not know	Fever or feverishness
cough		Numeric (categorical)	0 = No 1 = Yes 8 = Do not know	Cough
shortbreath		Numeric (categorical)	0 = No 1 = Yes 8 = Do not know	Shortness of breath
malaise		Numeric (categorical)	0 = No 1 = Yes	Malaise

⁷ If age in years not possible, please provide age in 5-year age groups.

Variable name	Collected by study site? (Please also indicate data source if not patient interview)	Type	Values and coding	Definition
			8 = Do not know	
myalgia		Numeric (categorical)	0 = No 1 = Yes 8 = Do not know	Myalgia
sorethroat		Numeric (categorical)	0 = No 1 = Yes 8 = Do not know	Sore throat
suddenonset		Numeric (categorical)	0 = No 1 = Yes 8 = Do not know	Sudden onset
headache		Numeric (categorical)	0 = No 1 = Yes 8 = Do not know	Headache
coryza		Numeric (categorical)	0 = No 1 = Yes 8 = Do not know	Coryza or rhinitis
Optional				
anosmia ⁸		Numeric (categorical)	0 = No 1 = Yes 8 = Do not know	Anosmia (Loss of sense of smell)
ageusia ⁹		Numeric (categorical)	0 = No 1 = Yes 8 = Do not know	Ageusia/dysgeusia (Loss or distortion of sense of taste)
Swabbing/testing information				
swabdate		Date	dd/mm/yyyy	Swabbing date
test_type		Numeric (categorical)	1 = PCR 2 = Point of care/rapid antigen test 3 = Other 8 = Do not know	Type of test used (if other, please specify)
lab_sarscov2		Numeric (categorical)	0 = Negative 1 = Positive 2 = Inconclusive 8 = Do not know	Laboratory result for SARS-CoV-2 (positive/negative)
lab_flu		Numeric (categorical)	0 = Negative 1 = Positive 2 = Inconclusive 8 = Do not know	Laboratory result for influenza (positive/negative)
lab_virusa		Numeric (categorical)	0 = Negative 1 = Positive 8 = Do not know	Laboratory result: virus type A

⁸ Anosmia and ageusia can also be combined into 'anosmia-ageusia'.

⁹ See above.

Variable name	Collected by study site? (Please also indicate data source if not patient interview)	Type	Values and coding	Definition
lab_virusb		Numeric (categorical)	0 = Negative 1 = Positive 8 = Do not know	Laboratory result: virus type B
lab_h1n1		Numeric (categorical)	0 = Negative 1 = Positive 8 = Do not know	Laboratory result: virus subtype AH1N1
lab_h3n2		Numeric (categorical)	0 = Negative 1 = Positive 8 = Do not know	Laboratory result: virus subtype AH3N2
byamagata		Numeric (categorical)	0 = Negative 1 = Positive 8 = Do not know	Laboratory result: B Yamagata lineage
bvictoria		Numeric (categorical)	0 = Negative 1 = Positive 8 = Do not know	Laboratory result: B Victoria lineage
Optional				
swabplace		Numeric (categorical)	1 = GP practice 2 = COVID-19 centre 3 = Self-swabbing 4 = Swab at home by healthcare worker 8 = Do not know	Place of swabbing (if relevant)
swab_type		Numeric (categorical)	1 = Nose 2 = Throat 3 = Both nose and throat 4 = Saliva 8 = Do not know	Type of swab taken
test_thisepisode		Numeric (categorical)	0 = No 1 = Yes 8 = Do not know	Have you already been tested for SARS-CoV-2 as part of this illness episode?
testtype_thisepisode		Numeric (categorical)	1 = PCR 2 = Point of care/rapid antigen test 3 = Other 8 = Do not know	If yes to above: What test type were you tested with (for this illness episode)?
testres_thisepisode		Numeric (categorical)	0 = Negative 1 = Positive 8 = Do not know	What was the test result (for this illness episode)?
gisaidid_sarscov2		Text		GISAID accession number for SARS-CoV-2

Variable name	Collected by study site? (Please also indicate data source if not patient interview)	Type	Values and coding	Definition
gisaidid_flu		Text		GISAID accession number for influenza
geneticvariant_sars cov2		Text		Genetic variant of SARS-CoV-2 virus using Pango nomenclature (can be collected separately at different date)
clade_flu		Text		Genetic variant of influenza virus (can be collected separately at different date)
Results for other respiratory pathogens (Optional, but RSV and seasonal coronavirus are recommended)				
lab_rsv ³		Numeric (categorical)	0 = Negative 1 = Positive 2 = Not done 8 = Do not know	Laboratory result for RSV (positive/negative)
lab_metapneum		Numeric (categorical)	0 = Negative 1 = Positive 2 = Not done 8 = Do not know	Laboratory result for human metapneumovirus (positive/negative)
lab_rhinovirus		Numeric (categorical)	0 = Negative 1 = Positive 2 = Not done 8 = Do not know	Laboratory result for rhinovirus (positive/negative)
lab_adenovirus		Numeric (categorical)	0 = Negative 1 = Positive 2 = Not done 8 = Do not know	Laboratory result for adenovirus (positive/negative)
lab_bocavirus		Numeric (categorical)	0 = Negative 1 = Positive 2 = Not done 8 = Do not know	Laboratory result for bocavirus (positive/negative)
lab_seascorona ⁴		Numeric (categorical)	0 = Negative 1 = Positive 2 = Not done 8 = Do not know	Laboratory result for seasonal coronavirus (positive/negative)
lab_enterovirus		Numeric (categorical)	0 = Negative 1 = Positive 2 = Not done 8 = Do not know	Laboratory result for enterovirus (positive/negative)
lab_parainfluenza		Numeric (categorical)	0 = Negative 1 = Positive 2 = Not done 8 = Do not know	Laboratory result for parainfluenza (positive/negative)

Variable name	Collected by study site? (Please also indicate data source if not patient interview)	Type	Values and coding	Definition
Vaccination variables				
covvaccany		Numeric (categorical)	0 = No 1 = Yes 8 = Do not know	COVID-19 vaccination status (any vaccination)
covvaccany_firstdose		Numeric (categorical)	0 = No 1 = Yes 8 = Do not know	COVID-19 vaccination status of first dose
covvaccany_seconddose		Numeric (categorical)	0 = No 1 = Yes 8 = Do not know	COVID-19 vaccination status of second dose
covvaccany_thirddose		Numeric (categorical)	0 = No 1 = Yes 8 = Do not know	COVID-19 vaccination status of third dose
covvaccany_4		Numeric (categorical)	0 = No 1 = Yes 8 = Do not know	COVID-19 vaccination status of fourth dose
covvaccdoses		Numeric (categorical)	0 = 0 doses 1 = 1 dose 2 = 2 doses 3 = 3 doses 4 = 4 doses 5 = 5 doses 99 = Do not know	COVID-19 vaccine doses
covvaccddate_firstdose		Date	dd/mm/yyyy	COVID-19 vaccination date of first dose
covvaccddate_seconddose		Date	dd/mm/yyyy	COVID-19 vaccination date of second dose
covvaccddate_thirddose		Date	dd/mm/yyyy	COVID-19 vaccination date of third dose
covvaccddate_4		Date	dd/mm/yyyy	COVID-19 vaccination date of fourth dose
covvaccddate_last ⁵		Date	dd/mm/yyyy	COVID-19 vaccination date of last dose
covvacbrand_firstdose		Text		Brand name of first dose COVID-19 vaccine
covvacbrand_seconddose		Text		Brand name of second dose COVID-19 vaccine
covvacbrand_third		Text		Brand name of third dose COVID-19 vaccine

Variable name	Collected by study site? (Please also indicate data source if not patient interview)	Type	Values and coding	Definition
covvacbrand_4		Text		Brand name of fourth dose COVID-19 vaccine
covvacbrand_last ⁶		Text		Brand name of last dose COVID-19 vaccine
fluvaccany		Numeric (categorical)	0 = No 1 = Yes 8 = Do not know	Received flu vaccination in current season
fluvaccdate		Date	dd/mm/yyyy	Influenza vaccination date
fluvaccype		Text		Type of vaccine (brand name)
fluvacc_n1		Numeric (categorical)	0 = No 1 = Yes 8 = Do not know	Received flu vaccination in previous season
Optional				
fluvacc_n2		Numeric (categorical)	0 = No 1 = Yes 8 = Do not know	Received flu vaccination in season before previous season (i.e. current – 2)
Underlying chronic conditions				
diabetes		Numeric (categorical)	0 = No 1 = Yes 8 = Do not know	Diabetes and endocrine disease
heart_dis		Numeric (categorical)	0 = No 1 = Yes 8 = Do not know	Heart disease
immuno		Numeric (categorical)	0 = No 1 = Yes 8 = Do not know	Immunodeficiency and organ transplant
lungdis		Numeric (categorical)	0 = No 1 = Yes 8 = Do not know	Chronic lung disease
obese		Numeric (categorical)	0 = No 1 = BMI ≥ 30 8 = Do not know	
Optional				
chronany_inf		Numeric (categorical)	0 = No 1 = Yes 8 = Do not know	Has a chronic condition that is associated with an influenza vaccination recommendation.
chronany_cov		Numeric (categorical)	0 = No 1 = Yes 8 = Do not know	Has a chronic condition that is associated with a COVID-19

Variable name	Collected by study site? (Please also indicate data source if not patient interview)	Type	Values and coding	Definition
				vaccination recommendation.
heart_disnohyp		Numeric (categorical)	0 = No 1 = Yes 8 = Do not know	Heart disease (excluding hypertension)
hyperten		Numeric (categorical)	0 = No 1 = Yes 8 = Do not know	Hypertension
lungdis_noasthma		Numeric (categorical)	0 = No 1 = Yes 8 = Do not know	Chronic lung disease excluding asthma
asthma		Numeric (categorical)	0 = No 1 = Yes 8 = Do not know	Asthma
cancer		Numeric (categorical)	0 = No 1 = Yes 8 = Do not know	Cancer
renal_dis		Numeric (categorical)	0 = No 1 = Yes 8 = Do not know	Renal disease
liver_dis		Numeric (categorical)	0 = No 1 = Yes 8 = Do not know	Liver disease
rheum_dis		Numeric (categorical)	0 = No 1 = Yes 8 = Do not know	Rheumatological disease
Possible exclusion criteria				
antivir		Numeric (categorical)	0 = No 1 = Yes 8 = Do not know	Administration of antivirals prior to swabbing
res_home		Numeric (categorical)	0 = No 1 = Yes 8 = Do not know	Living in a residential home
contra		Numeric (categorical)	0 = No 1 = Yes 8 = Do not know	Contra-indication for COVID-19 or influenza vaccination
pretest_cov		Numeric (categorical)	0 = No 1 = Yes 8 = Do not know	Has the patient had any positive SARS-CoV-2 test prior to this illness episode?
Optional				
antivirdate		Date	dd/mm/yyyy	Date administration antiviral
antivirtype		Text		Type of antiviral (brand name)

Variable name	Collected by study site? (Please also indicate data source if not patient interview)	Type	Values and coding	Definition
prevtest_type_cov		Numeric (categorical)	1 = PCR 2 = Rapid test 3 = Serology 3 = Other (please specify) 8 = Do not know	Type of test used to detect a previous episode of SARS-CoV-2
prevtest_date_cov		Date	dd/mm/yyyy	Date of most recent positive SARS-CoV-2 test prior to this illness episode?
prevtest_flu		Numeric (categorical)	0 = No 1 = Yes 8 = Do not know	Has the patient had a positive influenza test in the current influenza season?
Other variables				
gpvisit		Numeric (count)	integer	Number of GP consultations in the previous 12 months
pregnant		Numeric (categorical)	0 = No 1 = Yes 8 = Do not know	Pregnancy status
Optional				
severity		Numeric (count)	integer	Number of hospitalisations in the previous 12 months for the chronic disease
smoking			0 = Never 1 = Former 2 = Current 9 = Do not know	Never, former (stopped smoking at least 1 year before inclusion in the study), current smoker (any smoking can be included: cigarettes, cigars, vaping, etc.)

1. If age in years not possible, please provide age in five-year age groups.

2. Anosmia and ageusia can also be combined into 'anosmia ageusia'.

3. Optional, but highly desirable.

4. Optional, but highly desirable.

5. Study sites that are unable to provide dates of each vaccination can provide number of doses and the date and brand of last dose. It is highly recommended to also provide the brands of all doses (even if dates are not collected), or at a minimum just the brand of the first and last doses.

6. Study sites that are unable to provide brand of each vaccination can provide number of doses and the date and brand of last dose. It is highly recommended to also provide the brands of all doses (even if dates are not collected), or at a minimum just the brand of the first and last doses.

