3.7.3 Patient exclusion criteria

Patients are **excluded from the primary analysis** if they:

- refuse to participate in the study;
- are not swabbed;
- are unable to give informed consent or follow an interview in their native language because of aphasia, reduced consciousness, or other reasons;
- cannot be swabbed due to severe septum deviation, obstruction or other conditions that contra-indicate swabbing;
- have contraindications for the influenza (for IVE) or COVID-19 vaccination (for CVE);
- are institutionalised (virus exposure and risk factors may be different – specific cohort studies can be undertaken in these groups);
- are swabbed more than seven days (IVE) or 10 days (CVE) after symptom onset (to avoid false negatives; other numbers of days can be explored in sensitivity analyses);
- were vaccinated with a two-dose vaccine with fewer days between dose 1 and 2 than recommended by the manufacturer;
- had an inconclusive RT-PCR test.
- for IVE:
 - patients who had tested positive before to any influenza virus in the current season;
 - patients who had received antivirals 2 weeks prior to swabbing;

⁴ In certain circumstances, e.g. if COVID-19 testing centres are physician led, a consultation with a GP is not needed prior to the swab.

- for CVE:
 - patients who had tested previously positive to SARS-CoV-2 within 60 days prior to the current illness episode (other numbers of days and scenarios where date of previous test is unknown will be explored in sensitivity analyses);
 - controls positive to a seasonal coronavirus (e.g. HCoV-NL63, HCoV-229E, HCoV-OC43 and HCoV-HKU1) (as they may be affected by the vaccination).

Reasons for exclusion are documented.

Study sites can collect information on the exclusion factors and exclude patients according to available evidence on these factors.

In the main analysis, patients will be excluded if they were vaccinated with their most recent vaccine dose within 1–13 days preceding symptom onset (see section 3.8). In secondary analyses by time since vaccination, these patients could be included.

In sensitivity analyses, study sites can carry out the VE analyses with different cut-offs of numbers of days between onset and swabbing, using (for example) 5 and 7 days (see section 3.13.2).

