3.9.8 Previous influenza or SARS-CoV-2 infection

If information on previous influenza infection within the current influenza season is known, this can be documented and controls with this infection will be excluded from IVE analyses.

Among those patients consulting their GP with COVID-19-like symptoms, some may have already had a SARS-CoV-2 infection in the past. People who have been previously infected may have a greater response to the vaccine or be less likely to be reinfected even if unvaccinated. If possible, study sites will collect the following information:

- whether the patient had a previous positive SARS-CoV-2 test(s) (yes/no/unknown);
- optional:
 - type(s) of test: PCR, rapid test, serology (in case of multiple positive test results, the most recent);
 - date(s) of test (in case of multiple positive test results, the most recent);
 - history of COVID-19, e.g. clinical confirmation.

In the primary analysis, controls testing SARS-CoV-2 positive in the previous 60 days will be excluded from the analysis. Sensitivity analyses will be carried out including controls who previously tested SARS-CoV-2 positive, and stratifying by previous SARS-CoV-2 infection, if sample size allows. Additionally, if sample size allows and information is available, controls previously infected with SARS-CoV-2 will be included or excluded depending on differing days since last infection, or variant of infection.

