5.1.5 Previous infection in cases or controls

People who have been previously infected may have a stronger response to the vaccine or be less likely to be reinfected even if unvaccinated. It is possible that some of the controls (those testing negative for influenza/SARS-CoV-2) may have themselves been positive for influenza/SARS-CoV-2 some time before. The proportion of these (potentially immune individuals) in each country's dataset would depend on the circulation of the virus in the community in the months before the patient presented to the GP. Knowledge of their prior infection could affect their likelihood to be vaccinated. For example, if someone knew that they had had COVID-19, despite having no symptoms (e.g. if they had had a screening test), they may be subsequently less likely to be vaccinated. This would lower vaccination coverage among controls and decrease CVE. Similarly, if someone believed that they had

had influenza but had not had a test, they may be subsequently less likely to be vaccinated. This would lower vaccination coverage among controls and increase IVE.

Ascertainment of which controls may have had previous influenza/SARS-CoV-2 infection can be attempted by asking about previous influenza/SARS-CoV-2 tests and results, as well as prior clinical symptoms. However, there could potentially be several patients with prior SARS-CoV-2 or influenza infection, unbeknownst to them. Results should be interpreted in light of this, and an estimate of a range of potential bias should be calculated around the IVE and CVE estimates. Sensitivity analyses should be conducted including any patients with previous influenza (IVE) or SARS-CoV-2 (CVE) infection confirmed either by PCR or by serological tests.

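### Serology shares code 3 with 'Other' and counts without restriction as a previous positive SARS-CoV-2 test, so a blood-draw date can set days since infection, and previous-infection status can depend on vaccination

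*Protocol*

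**What the plan says.** Table A1 in Annex 1 codes `prevtest_type_cov` with 1 for PCR and 2 for rapid test, followed by "3 = Serology 3 = Other (please specify) 8 = Do not know", and defines it as "Type of test used to detect a previous episode of SARS-CoV-2". It is listed as optional, as is the date field `prevtest_date_cov`, defined as "Date of most recent positive SARS-CoV-2 test prior to this illness episode". The flag `pretest_cov` is not listed as optional and asks "Has the patient had any positive SARS-CoV-2 test prior to this illness episode".

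Section 3.9.8 lists the optional detail as "type(s) of test: PCR, rapid test, serology (in case of multiple positive test results, the most recent"), and the test date is likewise that of the most recent positive. Section 5.1.5 asks for sensitivity analyses that include patients with previous "infection confirmed either by PCR or by serological tests".

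For CVE, section 3.7.3 excludes from the primary analysis "patients who had tested previously positive to SARS-CoV-2 within 60 days prior to the current illness episode" and sends cases with an unknown test date to sensitivity analyses. Section 3.9.8 states the 60-day exclusion for controls only. Sections 3.7.3, 3.9.8 and 3.13.2 plan further analyses that include, exclude or stratify by previous infection and vary the delay since it.

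The protocol nowhere names an antibody target, limits the 60-day rule to virus-detection tests, or says how a positive serology in a vaccinated patient is handled.

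**The concern.** A positive antibody test differs from a positive PCR or antigen test in two ways that matter here.

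- **Timing.** Its date is that of the blood draw, not of the infection. A rule that counts days from the latest positive test of any type can therefore make an old infection look recent.
- **Dependence on exposure.** Depending on the assay, it may be positive because of vaccination. An unvaccinated seropositive patient has been infected. A vaccinated one may have been infected or only vaccinated. A 'previously infected' stratum built on such results compares unlike groups and pulls VE in that stratum down.

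The shared code adds a practical obstacle: an analyst of pooled data coded as in Annex 1 cannot set serology aside to check its influence. `test_type` and `testtype_thisepisode` in the same table use 3 for Other alone, so a 3 could easily be misread.

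At stake are mainly the sensitivity analyses on previous infection and time since infection, and to a lesser degree the primary CVE exclusion.

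**Working it through.** The protocol gives no figure on this point, so there is none to reproduce.

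**1. Codes.** `prevtest_type_cov` has five labels (PCR, rapid test, serology, other, do not know) and the codes 1, 2, 3, 3, 8, which are four distinct values. The request to specify 'Other' has no companion text field in Table A1.

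**2. The date rule, traced through.** Take a hypothetical patient with a positive PCR 200 days before the current episode and a positive serology 30 days before it. Sections 3.9.8 and Annex 1 keep the most recent positive, so the recorded delay is 30 days. Since 30 < 60, the patient is excluded as recently positive. By the PCR date, 200 > 60 and the patient stays in. The protocol's own definitions produce this, whatever the assay.

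**3. VE in a previously infected stratum.** All inputs are assumptions: true VE 50%; previous infection halves risk independently of vaccination; a share p = 0.4 of vaccinated seropositives truly infected; serology supplying a share s of the vaccinated patients' previous-positive records. Risks are relative to an unvaccinated, never-infected person.

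- Unvaccinated, previously infected: 0.50
- Vaccinated, truly infected: 0.5 × 0.5 = 0.25
- Vaccinated, seropositive: 0.5 × (0.4 × 0.5 + 0.6 × 1) = 0.40
- Stratum ratio: [(1 − s) × 0.25 + s × 0.40] / 0.50

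Results:

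- s = 0.10: 0.265 / 0.50 = 0.53, so VE reads 47%
- s = 0.20: 0.28 / 0.50 = 0.56, so VE reads 44%

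The correct stratum value is 1 − 0.25/0.50 = 50%.

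**4. Primary analysis.** Let f be the assumed share of vaccinated patients dropped because of a vaccine-induced positive serology within 60 days.

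If only controls are dropped (section 3.9.8), observed OR = true OR / (1 − f):

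| True VE | f = 1% | f = 5% | f = 10% |
|---|---|---|---|
| 30% | 29.3% | 26.3% | 22.2% |
| 60% | 59.6% | 57.9% | 55.6% |
| 80% | 79.8% | 78.9% | 77.8% |

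If the rule applies to all patients (section 3.7.3) and f is equal in vaccinated cases and controls, the factor cancels and VE is unchanged. Whether there is bias, and in which direction, therefore depends on which section is followed.

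**The case against.** The strongest reply is that this is a typing slip in an optional variable. Sites may use their own coding with a data dictionary (section 3.11.1). Section 5.1.5 uses serology to include patients in sensitivity analyses, not to exclude anyone, and asks for a range of potential bias to be calculated. The stratified analyses are done only if sample size allows. The choice of eligible test types could be left to a statistical analysis plan.

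Part of this stands: the variable is optional, and the affected analyses are mostly secondary. But the collision holds for every site that uses the Annex as printed. An analysis plan also cannot recover a PCR date that was never collected because a later serology took its place. A site that records only the `pretest_cov` flag cannot separate serology at all.

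Three stronger readings are tempting and are not supported:

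- *Serology, including undated results, drives the 60-day exclusion.* The protocol gives no frequency of serology, and section 3.7.3 assigns unknown dates to sensitivity analyses. Only a dated serology within 60 days can trigger the rule.
- *The duplicate code causes wrong exclusions.* The rule uses a positive result and its date, not the test type. The duplicate only blocks later separation.
- *Stratum VE could read 20% instead of 50%.* With p = 0.4 that is 1 − 0.40/0.50, which needs a stratum made up wholly of serology results. No section plans one.

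**Conclusion.** The point holds in a limited form and should be corrected. The protocol gives two test types one code, accepts serology without restriction as a previous positive test, and counts time from the most recent positive of any type. Followed as written, this can date an infection by a blood draw. Where the assay responds to vaccination, it also makes previous-infection status depend on the exposure.

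The size cannot be established from the document. Under the assumptions shown, VE in the previously infected stratum falls from 50% to about 44–47%. The effect on the primary analysis is probably small: none if exclusions fall equally on vaccinated cases and controls, and about 0.4 percentage points at a true VE of 60% if 1% of vaccinated controls alone are lost. Vaccine-induced positivity is an inference about the assay, on which the protocol is silent; the dating fault does not depend on it.

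**What to change.** - **Annex 1.** Recode `prevtest_type_cov` as 3 = Serology and 4 = Other. Limit `pretest_cov` to virus-detection tests, and reword `prevtest_date_cov` as the date of the most recent positive PCR or rapid antigen test. Add a separate optional yes/no item for positive serology, whose date is not used to time infection.
- **Sections 3.7.3 and 3.9.8.** Base the 60-day exclusion and all days-since-infection analyses on the most recent positive PCR or rapid antigen test.
- **Section 5.1.5.** Count positive serology as 'ever infected' in patients unvaccinated at the time of the blood test. In vaccinated patients, count it only if the assay target is known not to be vaccine-induced. Otherwise set previous infection to unknown.
- **Sections 3.7.3 and 3.9.8 together.** Reconcile whether the 60-day exclusion applies to all patients or to controls only.

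The cost is one recode, a few sentences and one extra optional item. It is not wholly free of new data: the assay target and a separate date for the last virus-detection test are not collected now. Where the target is not known, or it is unclear whether the blood test preceded vaccination, the serology result should be treated as uninformative. A few patients would move from excluded to included, or to unknown previous infection.
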